Transient increases in blood pressure and heart rate can be expected during line placement, needle sticks, blood draw, etc. and may also be attributed to anxiety/nervousness relating to a new environment. For most participants, only the initial recorded blood pressure and/or heart rate determines a subject’s qualification for the study. In the case where heart rate and blood pressure changes suggest participant discomfort or a potential safety concern, the participant will be removed from the study after qualifying, according to the discretion of medical and study staff.

- Venous and Arterial Access Screening:

An intravenous line needs to be placed in the subject’s hand or arm, and an arterial line in the radial artery of the subject’s wrist. The purpose of the intravenous line is to: (1) obtain venous blood samples for analysis (e.g., to verify subject meets inclusion criteria) and (2) intravenous fluid administration as needed. The purpose of arterial line is to: (1) obtain arterial blood samples for SpO₂-SaO₂ paired measurements and (2) blood pressure monitoring.

Prior to intravenous line placement, the intended site will be observed by the clinical staff to ensure there is no bruising (e.g., from any previous intravenous line placements); if there is bruising another location for line placement will be attempted.

Subjects will be given the option to have local anesthetics (such as lidocaine, ethyl chloride spray, and Pain Ease skin refrigerant spray) used at line placement sites to make line placement more comfortable.

Noninvasive ultrasound devices may be used to assist in line placement

The subject will be excluded from the study if the clinical team is unable to insert an intravenous line in the subject’s hand or arm and/or unable to insert an arterial line in the radial artery of the subject’s wrist.

- Blood Parameters Screening:

A venous blood sample will be obtained and analyzed to verify that the starting hemoglobin level is greater than or equal to 11.0 g/dL and carboxyhemoglobin (COHb) level is less than or equal to 3.0%. If hemoglobin level is less than 11.0 g/dL and/or COHb is greater than 3.0%, the subject will be excluded from the study.

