7.7.3.3. Blood Sampling Procedures

A qualified person will complete blood draws. These blood draws may occur at various points during the length of the study and may include qualifying blood samples, baseline blood samples before study procedures begin, and blood

samples after study procedures are complete to ensure the subject's wellbeing.

A set of blood samples of approximately 2 mL each will be drawn at selected time intervals throughout the study for laboratory analysis. The blood sample will be collected in vacutainer tubes or syringes for analysis by standard laboratory methods which may include co-oximetry and analysis by other point of care devices.

The total amount of blood drawn during study participation will not exceed 400 mL (which is less than the standard amount in a blood donation).

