8.1.2. Sample size

 This study will target a minimum of 18 subjects but may be modified based on actual numbers required to maintain adequate power for the study. Depending

on dropout rates, additional subjects may be enrolled to obtain sufficient representative data for factors such as sex, skin pigmentation, oxygen saturation, and other factors as required.

The final A_{RMS} analysis will utilize statistical methods to ensure performance statistics are calculated with comparable density over the range 70-100% SaO₂ and account for multiple samples per subject. Statistical analysis for each subgroup will be performed to show differences in biases among different subgroups.

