8.2. Data Analysis

8.2.1. Accuracy Calculations

Accuracy will be reported as the Bias, Precision, and A_{RMS} using the following equations:

$$Bias = \frac{1}{n} \sum_{i=1}^n (SpO_{2i} - SaO_{2i})$$

$$Precision = \sqrt{\frac{\sum_{i=1}^n (SpO_{2i} - SaO_{2i} - Bias)^2}{n - 1}}$$

$$A_{RMS} = \sqrt{\frac{\sum_{i=1}^n (SpO_{2i} - SaO_{2i})^2}{n}}$$

The A_{RMS} will be adjusted to account for repeated measurements on each subject.

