8.2.2. Acceptance Criteria

- SpO₂: A_{RMS} ≤ 2% over the range 70-100%, under no motion.

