8.2.3. Exclusion Criteria

The following data exclusion criteria will be applied before statistical analysis.

Data will be excluded in the event:

- Either reference or test device does not provide data.
- Incomplete study or early termination, where the desaturation protocol could not be completed.
- Reference device malfunctions and/or provides inconsistent saturation values.
- Discontinuities and abrupt dropouts due to instruments recalibration or device failure.
- Low signal quality, e.g., due to noise or interference. Specifically, the INOP Indicators with <SpO₂ Labels> : Chk Sensor, Extd, Update, Interference, Low Perf, and Poor Signal will be used for data exclusion.
- Subject's oxygen saturation is unstable. This is determined using multiple (up to 5) consecutive blood draws, to be stable within 1% to 2% SaO₂ of neighboring draws (as obtained from a reference device) to include the measurement pair.
- Exclusion of subjects that do not have desaturation points in the lowest saturation bin (70-80%).
- Exclusion of data to statistically equalize samples per subject, and across the 70-100% saturation bins.

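### Section 8.2.3 balances bins and subjects by discarding valid SpO₂-SaO₂ pairs; weighting all valid pairs gives the same balance with a somewhat smaller standard error at almost no cost

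*Combined protocol and SAP*

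**What the plan says.** Section 8.2.3 lists data exclusions and states that "The following data exclusion criteria will be applied before statistical analysis". Most bullets concern data quality: missing readings, malfunction, poor signal, and unstable saturation judged from "multiple (up to 5) consecutive blood draws". One removes subjects with no points in the 70-80% bin. The last has a different purpose: "Exclusion of data to statistically equalize samples per subject, and across the 70-100% saturation bins". No target count or rule for choosing the pairs to drop is visible.

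Section 8.1.2 says that statistical methods will ensure that "performance statistics are calculated with comparable density over the range 70-100% SaO₂ and account for multiple samples per subject", without naming a method. Section 8.2.1 prints unweighted formulas for Bias, Precision and ARMS and adds that ARMS "will be adjusted to account for repeated measurements on each subject", again without a method. Section 8.2.2 sets the acceptance limit at ARMS of at most 2% "over the range 70-100%, under no motion".

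**The concern.** The plan is coherent: once counts are equal, the unweighted ARMS of section 8.2.1 is a balanced figure. The weakness lies in how balance is reached. Valid pairs are removed before analysis, and nothing named later in the plan can bring them back.

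Acceptance compares a point estimate with a fixed limit and no margin. Avoidable noise therefore makes it less likely that a device just inside the limit passes and more likely that one just outside it does. If no selection rule is fixed, the result also depends on which pairs happen to be dropped. Each pair needs an arterial sample: section 7.7.2.2 gives one purpose of the arterial line as to "obtain arterial blood samples for SpO₂-SaO₂ paired measurements", and section 7.7.3.3 puts each sample at about 2 mL.

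**Working it through.** **Inputs from the documents:** 18 subjects (section 8), limit 2% (8.2.2), lowest bin 70-80% (8.2.3). **Assumed, because the documents do not give them:** three bins, pairs per subject-bin cell uniform over a stated range, normal errors with no bias, and random deletion. The share of variance between subjects is *a*, and the share between bins within a subject is *b*. The plan has no figure of its own on this point to reproduce.

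**1. Same target.** Let cell *i* hold nᵢ squared differences, and let a random *k* of them be kept. Averaged over all possible choices, the mean of the kept values equals the mean of all nᵢ. The equally weighted mean square is thus the average of the deleted mean square over all deletions: same expectation, no larger variance. This does not depend on the assumed variances or counts.

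**2. Size, strict reading (all 18 × 3 = 54 cells cut to the smallest).** With total variance σ²,

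Var(mean square) = 2σ⁴ { a²/18 + [(a+b)² − a²]/54 + [1 − (a+b)²]·h/54 },

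where h is the mean of 1/nᵢ under weighting and 1/k under deletion. To first order, the ratio of ARMS standard errors is the square root of the variance ratio.

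For 5-10 pairs, h = (1/5 + 1/6 + 1/7 + 1/8 + 1/9 + 1/10)/6 = 0.1409, against 1/k = 0.2:
- a = 0.1, b = 0: (0.000556 + 0.99 × 0.2/54) / (0.000556 + 0.99 × 0.1409/54) = 0.004222/0.003139; square root 1.160.
- a = 0.2, b = 0.5: 0.012444/0.011887; square root 1.023.

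Simulation (20,000 datasets per entry) agrees. Standard error after deletion divided by weighted standard error:

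| Pairs per cell | Pairs deleted | a,b = 0.1,0 | 0.2,0 | 0.3,0 | 0.2,0.3 | 0.2,0.5 |
|---|---|---|---|---|---|---|
| 7-10 | 81 of 459 (18%) | 1.076 | 1.051 | 1.026 | 1.022 | 1.008 |
| 5-10 | 135 of 405 (33%) | 1.163 | 1.100 | 1.069 | 1.051 | 1.024 |
| 3-12 | 243 of 405 (60%) | 1.380 | 1.265 | 1.183 | 1.127 | 1.067 |

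Under full independence (a = b = 0), which section 8.1.1 assumes, the formula gives √(0.2/0.1409) = 1.19 for 5-10 pairs and 1.09 for 7-10. With a = 0.7, b = 0 the increase falls to about 1% and 0.4%.

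**3. Milder reading (only subject totals and bin totals equalized).** Deletion falls to 13%, 23% and 39% of pairs, and the standard error rises by 1-6%, 2-11% and 4-16% for the three count ranges.

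**4. Fixed counts.** If every subject has 5/7/10 pairs in the low/middle/high bin, 7 of 22 (32%) are deleted. With bin RMS in the ratio 2.6/1.8/1.5 the standard error rises by only 1-4%.

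**5. Effect on the verdict (strict reading, 5-10 pairs).** Ranges run over the five variance settings in the table.

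| True ARMS | One random deletion and the weighted estimate disagree on pass/fail |
|---|---|
| 2.0 | 7-17% of datasets |
| 1.9 | 5-8% |
| 1.8 | 1-2% |
| 1.6 | 0-0.1% |

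At 1.9 the pass probability falls by 0.5-3 points (77.1 to 76.6%, up to 91.2 to 88.1%). At 2.1 the false-pass probability rises by 0.4-4 points (28.9 to 29.3%, up to 11.6 to 15.6%).

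**6. Why the bullet cannot simply go.** With bin RMS 2.6/1.8/1.5, equal bins give √[(6.76 + 3.24 + 2.25)/3] = 2.02. The unweighted formula with counts 5:7:10 gives √[(5 × 6.76 + 7 × 3.24 + 10 × 2.25)/22] = 1.89. The two fall on opposite sides of the limit.

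**The case against.** The strongest reply is that this is a preference between two valid ways of balancing, with a small gain. The upper figures need the strict reading and weak correlation. The wording fits equal subject and bin totals at least as well, and consecutive draws at one saturation level are probably correlated, which points to the low end. That stands, and it limits the size of the point.

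Part of section 8.1.2 is not visible in the public version, and its unnamed methods might include repeated subsampling with averaging. Averaging mean squares over all deletions is the weighted estimate, so the loss would vanish. The pass/fail disagreement figures apply only to a single random deletion. This also stands, but the visible rule is exclusion before analysis. A hidden selection rule would remove the arbitrariness of the choice, not the loss of information.

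The simulations use ARMS without the unspecified repeated-measures adjustment, so the exact percentages may differ for the final statistic. Sparse cells receive large per-pair weights, and a subject with no pairs in a bin carries less total weight; deletion has trouble with empty cells too. The blood-sample argument is minor: the change saves no draws, and a draw whose pair is excluded can still help to show that a neighbouring draw is stable.

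None of this reverses the direction. Under random deletion, weighting cannot do worse for the same balanced target.

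**Conclusion.** The point holds as a worthwhile, low-cost improvement, not as an error that invalidates the plan. Deleting valid pairs to equalize counts gives up precision that weighting keeps. The loss is about 1-16% of the standard error with 5-10 or 7-10 pairs per cell across the variance settings tabulated, and 1-11% under the milder reading. It is larger if counts are very uneven (up to 38% with 3-12 pairs, strict reading). The direction rests only on random deletion and pairs being exchangeable within a cell. The size rests on assumed counts, variance shares and three bins. The practical effect is small near the 2% limit and negligible at a true ARMS of 1.6 or less. The sample size of 18 is not affected.

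**What to change.** Replace the last bullet of section 8.2.3 with wording such as:

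> All pairs that pass the quality criteria are kept. Bias, Precision and ARMS are computed with pre-specified weights: each saturation bin has equal total weight and, within each bin, each contributing subject has equal weight. Bin limits are fixed in advance.

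In section 8.2.1 print the matching formulas:
- ARMS: square root of the mean over bins of the mean over contributing subjects of the subject's mean squared SpO₂-SaO₂ difference in that bin.
- Bias: the same average of the plain differences.
- Precision: √(ARMS² − Bias²), so that the three figures agree. This replaces the n − 1 form.

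The repeated-measures adjustment stays; state how it is applied to the weighted estimate. If deletion is kept, make it a sensitivity analysis with target count, random rule and seed fixed in advance, and report how many pairs are dropped.

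**Cost:** SAP wording and a few lines of code; no extra subjects or draws. The downside is the large weight on cells with one or two pairs. With 1-10 pairs per cell the weighted standard error was 0.108-0.142, against 0.089-0.139 for the unweighted, unbalanced ARMS on all pairs, and 0.194-0.207 after deletion to the smallest cell.

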8.2.4. Expected Dropout Rates

Subjects may not complete the study for various reasons, such as a clinical screening test failure, at the investigator's or study staff's discretion, or because the subject does not want to continue the study. However, the sample size per group may be increased to account for dropout rates during the study.

9. DATA MANAGEMENT

9.1. Data Management and Confidentiality

All documents associated with this protocol will be securely stored in a physical location or on password-protected computers. The confidentiality and retention of these documents will be protected to the extent provided and required by the law. All data will be de-identified before any statistical analysis. Only de-identified data will be shared with Masimo for research purposes stated in this protocol. Data collected by the eCRF data capture software will be shared with Masimo via a secure, password-protected server that only study staff and Masimo study team members will have access to. Data will be retained for a minimum of two years following completion of the final analysis.

9.2. Source Documents

Source data is all information, original records of clinical findings, observations, or other activities in a clinical trial necessary for the reconstruction and evaluation of the trial. Source data are contained in source documents. Examples of these original documents and data records include hospital records, clinical and office charts, laboratory notes, memoranda, recorded data from automated instruments, and copies or transcriptions certified after verification as being accurate and complete.

9.3. Case Report Forms

The site shall capture study data in case report forms (CRFs) for each subject enrolled, to be provided to the sponsor. CRFs may be in paper or electronic format through electronic data capture (EDC) software. Masimo shall ensure that systems used for electronic CRFs are compliant with the requirements of 21 CFR Part 11 and ISO / IEC 27001 certification. The CRFs will be completed and signed by the PI or delegate. This also applies to those subjects who fail to complete the study.

If a subject withdraws from the study, the reason must be noted on the CRF. The eCRFs are to be completed on an ongoing (weekly) basis. CRF entries and corrections will only be performed by study site staff, authorized by the investigator. For paper CRFs, entries and corrections to the CRF will be made following good documentation practices (GDP).

The CRF may include the following information, including but not limited to: inclusion/exclusion criteria, demographic information, device readings, occurrence of any adverse events and protocol deviation, and device deficiencies, if any. The CRFs will be signed by the PI or delegate to attest that the data are complete and accurate.

CRF entries will be checked by the study monitor and any errors or inconsistencies will be queried to the site on an ongoing basis. Any changes made within an electronic CRF will be tracked by audit trail. Any changes on a paper CRF will be made directly on the CRF and will be initialed and dated by the person making the change. Query resolution will be assessed and confirmed by study monitor during site visit.

9.4. Data Transfer and Storage

Original paper CRFs will be stored in a secure location at the site. Copy of the original paper CRFs may be scanned and sent to sponsor. If using electronic CRFs, the site staff will be assigned unique usernames and passwords for data security. Final copies of the electronic CRFs in EDC are stored on a secure server.

Only authorized sponsor personnel will have access to study data and will move it to a secure and backed-up drive at Masimo.

CRFs will be checked for completeness and if there are inconsistent or missing data points, queries will be generated. If delegated study staff are to correct the paper CRF, they shall follow GDP practices to strike through old entry, add in new entry, initial and date it, and provide the corrected information to sponsor. Corrections made to electronic CRFs will be tracked by audit trail and require PI or delegate sign-off.

9.5. Record Retention

Study data will be retained for the necessary period of time as required by regulations. Study records shall be retained for a minimum of two years after study closure.

10. AMENDMENTS TO THE CLINICAL INVESTIGATION PLAN

Any changes made to the clinical investigational plan/study protocol will be documented by way of an amendment. Before submitting a protocol amendment to the IRB, the protocol amendment must be agreed upon and signed by both the PI and the sponsor. The protocol amendment will be submitted to the IRB for approval. At a minimum, a redline version and a clean version of the new protocol amendment will be kept on file by the PI and the sponsor. Protocol amendments will need to be version controlled. Both PI and sponsor will retain the IRB approval letter as confirmation that the protocol amendment was approved.

11. DEVIATIONS FROM CLINICAL INVESTIGATION PLAN

Deviations from the protocol must receive both sponsor and the investigator's IRB/ethics committee approval before they are initiated, with the exception that under emergency circumstances, deviations from the *Clinical Investigation Plan* to protect the rights, safety and well-being of human subjects may proceed without prior approval of the sponsor or the IRB/ethics committee.

Any protocol deviations initiated without sponsor and the investigator's IRB/ethics committee approval that may affect the scientific soundness of the study, or affect the rights, safety, or welfare of study subjects, must be documented and reported to the sponsor and to the investigator's IRB/ethics committee as soon as a possible, but no later than 5 working days after the occurrence of the protocol deviation. In addition to documenting deviations on the CRF, the *Protocol Deviation Form* may also be used. If protocol deviations continue to occur frequently at a study site, a corrective and preventive action (CAPA) may be opened by the sponsor.

Withdrawal of IRB approval: An investigator shall report to the sponsor a withdrawal of approval by the investigator's reviewing IRB as soon as possible, but no later than five working days of the IRB notification of withdrawal of approval.

12. DEVICE ACCOUNTABILITY

12.1. Receipt of Study Device

Upon receipt of the study device supplies, an inventory must be performed and the device accountability log filled out and signed by the person accepting the shipment. It is important that the designated study staff counts and verifies that

the shipment contains all the items noted in the shipment inventory. Any damaged or unusable study devices in a given shipment will be documented in the study files. The investigator must notify the study sponsor of any damaged or unusable study devices that were supplied to the investigator's site.

12.2. Use of Study Device

Use of device will be documented in a CRF module for each subject. Any unused devices must be returned to the sponsor at the end of the study or before product expiration date.

12.3. Return or Destruction of Study Device

At the completion of the study, there will be a final reconciliation of study devices shipped, devices used, and devices remaining. This reconciliation will be logged on the device accountability log. Any discrepancies noted will be investigated, resolved, and documented prior to return or destruction of unused study devices. Devices destroyed onsite will only be upon written instruction from the sponsor and will be documented in the study files. When a Masimo device deficiency is observed, every effort should be made to return the device and its packaging to the sponsor in a timely manner.

13. STATEMENTS OF COMPLIANCE

This document is a clinical investigational plan for a human research study sponsored by Masimo Corporation. The study will be conducted in accordance with the ethical principles that have their origin in the Declaration of Helsinki. By participating in the study, the Investigator agrees to adhere to all stipulations of this protocol, the conditions of the IRB or Research Ethics Committee approval, federal and local regulatory requirements, 21 CFR 812, ISO-14155, ICH GCP guidance.

The protocol, ICFs, recruitment materials, and all subject materials will be submitted to the IRB for review and approval. Approval of both the protocol and the consent form must be obtained before any subject is enrolled. Any amendment to the protocol will require review and approval by the IRB before the changes are implemented to the study.

14. INFORMED CONSENT PROCESS

See subsection on Informed Consent under *Study Procedures*.

15. ADVERSE EVENTS, ADVERSE DEVICE EFFECTS, AND DEVICE DEFICIENCIES

15.1. Definitions

The definitions for adverse event, adverse device effect, serious adverse event, serious health threat, serious adverse device effect, and unanticipated adverse device effect, device deficiencies are provided below (ISO 14155, 21 CFR 812.3(s)).

- adverse event: untoward medical occurrence, unintended disease or injury, or untoward clinical signs (including abnormal laboratory findings) in subjects, users or other persons, whether or not related to the investigational medical device and whether anticipated or unanticipated (ISO 14155)
- adverse device effect: adverse event related to the use of an investigational medical device
- serious adverse event: adverse event that led to any of the following:
 - a) death

- b) serious deterioration in the health of the subject, users, or other persons as defined by one or more of the following:
 - 1) a life-threatening illness or injury, or
 - 2) a permanent impairment of a body structure or a body function including chronic diseases, or
 - 3) in-subject or prolonged hospitalization, or
 - 4) medical or surgical intervention to prevent life-threatening illness or injury, or permanent impairment to a body structure or a body function,
- c) fetal distress, fetal death, a congenital abnormality, or birth defect including physical or mental impairment

Note: Planned hospitalization for a pre-existing condition, or a procedure required by the *Clinical Investigation Plan*, without serious deterioration in health, is not considered a serious adverse event.

- serious health threat: signal from any adverse event or device deficiency that indicates an imminent risk of death or a serious deterioration in the health of subjects, users or other persons, and that requires prompt remedial action for other subjects, users or other persons.

Note: This would include events that are of significant and unexpected nature such that they become alarming as a potential serious health hazard or possibility of multiple deaths occurring at short intervals.

- serious adverse device effect: adverse device effect that has resulted in any of the consequences characteristic of a serious adverse event
- unanticipated serious adverse device effect: serious adverse device effect which by its nature, incidence, severity or outcome has not been identified in the current risk assessment

Note: Anticipated serious adverse device effect (ASADE) is an effect which by its nature, incidence, severity or outcome has been identified in the risk assessment.

- device deficiency: inadequacy of a medical device with respect to its identity, quality, durability, reliability, usability, safety or performance

Note 1: Device deficiencies include malfunctions, use errors, and inadequacy in the information supplied by the manufacturer including labeling.

Note 2: This definition includes device deficiencies related to the investigational medical device or the comparator.

